ATTACHMENT 6. : HRS DERIVATION

The HRS categories should be evaluated from 6 to 1. First check if the subject falls in category 6 (has the subject died?) if not then we evaluate category 5, if not 5 then evaluate category 4 and so on.

The HRS is evaluated at baseline and per day, relative to the first study drug intake.

The baseline HRS is covering the full baseline/screening/day 1 visit which can occur on 2 days.

Timing of first study drug intake is not taken into account.

Note:

- VSOXYSAT is assessed 3 times per day (or per baseline visit). In case one of the assessments says 'N' then the final result for that day (or baseline visit) is 'N', else if one of the assessments is 'NA' then the final result is 'NA' else if one of the assessments is missing then final result is missing.

So a combination of 'Y', "", "N" → result ='N'

'Y', "", "NA" → result ='NA'

'Y','Y','' → result =''

'Y','Y','Y' → result ='Y'

On the baseline visit, on days at or after HO end date or on the day of discontinuation it might be that less than 3 assessments are done. Therefore, take only the records into account from the dataset on those days as planned. The same rules above apply to derive the final result per day when more than 1 assessment is collected.

- In case the subject withdrew from the study, the HRS will be set to missing from the next day onwards.
- In case of chronic oxygen use and multiple CMARTN values on a day we consider the worst value: In case one of the values is 'N' then final result for that day (or baseline visit) is 'N', else if one of the assessments is missing then final result is missing.
- The list of types of supplemental oxygen and invasive mechanical ventilation can be extended depending on the medical review (see DPS part 2 or Excel sheet of the medical review)
- The list of hospitalization terms (i.e.: ICU or WARD) can be extended depending on the medical review (see DPS part 2 or Excel sheet of the medical review).
- If the Subjects has no HO data, the subject is considered to be in the hospital during the trial. All other aspect of the HRS will be evaluated according to the derivation below.
- In case the readiness for discharge (RDISHOSP) is assessed more than once per day (baseline visit) we consider the worst value: in case one of the values is 'N' then the final result of that day (or baseline visit) is 'N'

Some clarification is required for following categories:

6. Death

When DM.DTHDTC<=(date of assessment)

5. Requiring invasive mechanical ventilation;

When CMSTDTC<=(date of assessment) <=CMENDTC where CMADMTP="INVASIVE MECHANICAL VENTILATION"

And CMADMDS in ('Through Endotracheal tube' 'Through Tracheostomy tube' or 'Through ECMO')

4. Admitted to the ICU;

From the HO data set:

hostdy <=(day of assessment)<=hoendy
hoterm = 'ICU'

From the SS data set:

SSTESTCD= 'REQICU' and SSSTRESC='Y'
Or SSTESTCD= 'REASICU' and SSSTRESC='Y'
Or both REQICU and REASICU is missing and NOT (RDISHOSP = 'Y' on the day of assessment and RDISHOSP = 'Y' on the day (baseline visit) before)

OR

From the HO data set:

hostdy <=(day of assessment)<=hoendy
hoterm = 'WARD'

From the SS data set:

SSTESTCD='REASICU' and SSSTRESC='Y'
OR
SSTESTCD='REQICU' and SSSTRESC='Y'

3. Non-ICU hospitalization, requiring supplemental oxygen

Non-ICU hospitalization:

hostdy <=(day of assessment)<=hoendy
hoterm = 'Hospital inpatient Department (WARD)'
NOT (RDISHOSP='Y' on the day of assessment and RDISHOSP='Y' on day(baseline visit) before)

OR

hostdy <=(day of assessment)<=hoendy
hoterm = 'ICU'
NOT (RDISHOSP='Y' on the day of assessment and RDISHOSP='Y' on day(baseline visit) before)

OR

(day of assessment)=hoendy+1
RDISHOSP='N' on day(baseline visit) before

OR

In case re-hospitalization occurred (there is a day between the HOENDY of the previous record and HOSTDY of the next record)
(day of assessment) =HOSTDY (of the re-hospitalization)
NOT (RDISHOSP='Y' on the day of assessment and RDISHOSP='Y' on day(baseline visit) before)

AND

Requiring supplemental oxygen:

'Receiving supplemental oxygen through a face mask or nasal cannula and not being able to sustain a blood oxygen saturation of $\geq 94\%$ when breathing room air for 15 minutes at any time on the day of assessment.'

FAOBJ=CHRONIC OXYGEN USE and FAORRES='N'

CMADMTP in ("Non-Invasive Mechanical Ventilation", "Nasal Cannula", "Venturi Mask", "Simple Face Mask", "Nonrebreathing Face Mask with Reservoir and One-Way Valve".)

CMTRT=SUPPLEMENTAL OXYGEN and CMSTDTC <= date of assessment <= CMENDTC

VSOXYSAT in ('N' 'NA') at any time during the day of assessment (OR is missing)

OR

'If supplemental oxygen was provided chronically pre-influenza infection (based on medical history), that amount of supplemental oxygen is exceeded to prevent hypoxia, tachypnea or dyspnea at some point on the day of assessment.'

FAOBJ=CHRONIC OXYGEN USE and FAORRES='Y'

CMARTN = 'N'

CMADMTP in ("Non-Invasive Mechanical Ventilation", "Nasal Cannula", "Venturi Mask", "Simple Face Mask", "Nonrebreathing Face Mask with Reservoir and One-Way Valve".) and CMTRT=SUPPLEMENTAL OXYGEN and CMSTDTC <= date of assessment <= CMENDTC

OR

'Not receiving supplemental oxygen and Having a blood oxygen saturation of <94% when breathing room air for 15 minutes at any measurement on the day of assessment'

No record in cm with oxygen supplementation

VSOXYSAT='N' at any time on the day of assessment OR [VSTESTCD='OXYSAT' and VSORRES<94% and VSOXSMRA='Y']

OR

'Not receiving supplemental oxygen and in case of known pre-influenza SpO2 <94% (eg, due to COPD), the current blood oxygen saturation on room air is lower than pre-influenza infection levels by at least 3%.'

No record in cm with oxygen supplementation

VSEVINTX= PRE-INFLUENZA INFECTION and VSTESTCD='OXYSAT' and 'VSORRES<94% and VSRMAIR='Y'

VSORRES and VSTESTCD=OXYSAT (of day of assessment) < [VSORRES and VSEVINTX= PRE-INFLUENZA INFECTION and VSTESTCD='OXYSAT' and VSRMAIR='Y' - 3]

2. Non-ICU hospitalization, not requiring supplemental oxygen

hostdy <=(day of assessment)<=hoendy

hoterm = 'Hospital inpatient Department (WARD)'

NOT (RDISHOSP='Y' on the day of assessment and RDISHOSP='Y' on day(baseline visit) before)

hostdy <=(day of assessment)<=hoendy

hoterm = 'ICU'

NOT (RDISHOSP='Y' on the day of assessment and RDISHOSP='Y' on day(baseline visit) before)

OR

(day of assessment)=hoendy+1

RDISHOSP='N' on day(baseline visit) before

OR

In case re-hospitalization occurred (there is a day between the HOENDY of the previous record and HOSTDY of the next record)

(day of assessment) =HOSTDY (of the re-hospitalization)

NOT (RDISHOSP='Y' on the day of assessment and RDISHOSP='Y' on day(baseline visit) before)

1. Not hospitalized

Some examples

Discharge against medical advice

If a subject is discharged 'against medical advice' on the day prior to the day of assessment, the subject will be considered as hospitalized (evaluating the others aspects of the HRS to define the correct category, e.g.: requiring supplemental oxygen, on the day of assessment)

We have a discharged against medical advice if on the day the subject is discharged (according to the HO dataset) the investigator indicated he is not ready and his SS status is discharged,

	Day 3	Day 4	Day 5	Day 6	Day 7	Day 8
Status (HO)	Hospitalized	Hospitalized	Hospitalized	Discharged	Home	Home
Case 1						
ready (SS)	Not ready	Not ready	Not ready	Not ready	--	--
Status(SS)	hospitalized	hospitalized	hospitalized	Hospitalized	discharged	--
Against medical advice?					NO	
HRS	>1	>1	>1	>1	>1	HOME
Case 2						
ready (SS)	Not ready	Not ready	Not ready	Not ready	Ready	--
Status(SS)	hospitalized	hospitalized	hospitalized	Hospitalized	discharged	--
Against medical advice?					NO	
HRS	>1	>1	>1	>1	>1	HOME
Case 3						
ready (SS)	Not ready	Not ready	Not ready	Not ready	Not ready	--
Status(SS)	hospitalized	hospitalized	hospitalized	Hospitalized	discharged	--
Against medical advice?					NO	
HRS	>1	>1	>1	>1	>1	HOME
Case 4						
ready (SS)	Not ready	Not ready	Not ready	Not ready		--
Status(SS)	hospitalized	hospitalized	hospitalized	Discharged		

Against medical advice?				YES		
HRS	>1	>1	>1	>1	>1	Missing
Case 5						
ready (SS)	Not ready	Not ready	Not ready	Ready	--	--
Status(SS)	hospitalized	hospitalized	hospitalized	discharged		
Against medical advice?				NO		
HRS	>1	>1	>1	>1	HOME	HOME
Case 6						
ready (SS)	Not ready	Not ready	Not ready	Ready	--	--
Status(SS)	hospitalized	hospitalized	hospitalized	hospitalized	discharged	
Against medical advice?				NO		
HRS	>1	>1	>1	>1	HOME	HOME
Case 7						
ready (SS)	Not ready	Not ready	Ready	Ready	--	--
Status(SS)	hospitalized	hospitalized	hospitalized	hospitalized	discharged	
Against medical advice?				NO		
HRS	>1	>1	>1	HOME	HOME	HOME
Case 8						
ready (SS)	Not ready	Not ready	Not ready	--	--	--
Status(SS)	hospitalized	hospitalized	discharged	--	--	
Against medical advice?			NO			
HRS	>1	>1	>1	>1	HOME	HOME

Only in case 4 above we have a discharge against medical advice which would lead to missing values from day 8 onwards. The HRS on day 7 is defined by the other aspects of the HRS (requiring oxygen, ICU,..) on day 7 and not copied from day 6.

Requiring supplemental oxygen

	Case 1	Case 2	Case 3	Case 4	Case 5	Case 6
supplemental oxygen (CM)	YES	YES	NO	NO	NO	NO
Chronic oxygen use	No	yes	Not used	Not used	Not used	Not used
returned to prior level?	Not used	N	Not used	Not used	Not used	Not used
pre influenza infection levels	Not used	Not used	Not used	Not used	Not used	93
Oxysat record < pre-influenza level at any moment during the day	Not used	Not used	Not used	Not used	Not used	yes
sustain >94% Oxy sat (VSOXYSAT)	N' missing or 'NA'	N' missing or 'NA'	N' at any time during the day	Missing or NA	YES	Not used
Oxysat record <94% at any moment during the day	Not used	Not used	no	yes	yes	Not used

REQUIRING SUPPLEMENTAL OXYGEN?	YES	YES	YES	YES	YES	YES
--------------------------------	-----	-----	-----	-----	-----	-----

To pay attention to

	Case 7	Case 8	Case 9	Case 10	Case 11	Case 12
supplemental oxygen (CM)	YES	No	No	YEs	YEs	YEs
Chronic oxygen use	No	Not used	Yes	Yes	Yes	Yes
returned to prior level?	Not used	Not used	N	Missing	N	y
pre influenza infection levels	Not used	93	Not used	Not used	Not used	Not used
Oxysat record < pre-influenza level at any moment during the day	not used	yes	Not used	Not used	Not used	Not used
sustain >94% Oxy sat (VSOXYSAT)	missing	yes	Missing	Missing	Yes	Yes
Oxysat record <94% at any moment during the day	yes	Not used	Missing	Not used	Not used	yes

REQUIRING SUPPLEMENTAL OXYGEN?	NO	YES	NO	YES	YES	NO
--------------------------------	----	-----	----	-----	-----	----

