10.3. Withdrawal From the Study

A subject will be automatically withdrawn from the study for any of the following reasons:

- Lost to follow-up.

- Withdrawal of consent/assent.
- Death.

If a subject is lost to follow-up, every reasonable effort must be made by the study site personnel to contact the subject and determine the reason for discontinuation/withdrawal. The measures taken to follow up must be documented.

When a subject withdraws before completing the study, the reason for withdrawal is to be documented in the eCRF and in the source document. Study drug assigned to the withdrawn subject may not be assigned to another subject. No additional subjects will be enrolled for subjects who withdraw early. If a subject withdraws from the study before the end of the treatment or the follow-up phase, he or she will be offered an optional Safety Follow-up Visit. The optional Safety Follow-up Visit will occur on the day of withdrawal or on the day after and will consist of the same assessments as at the Final Study Visit (Day 28), with optional PRO completion.

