5.2. Primary Efficacy Endpoint(s)

5.2.1. Definition

The primary efficacy analysis will be based on the ITT-i analysis set and consists of the analysis of the hospital recovery scale outcome on Day 6.

The hospital recovery scale provides 6 mutually exclusive conditions ordered from best to worst, and the score reflects the subject’s worst situation on the day of assessment:

1. Not hospitalized
2. Non-ICU hospitalization, not requiring supplemental oxygen
3. Non-ICU hospitalization, requiring supplemental oxygen
4. Admitted to the ICU, not requiring invasive mechanical ventilation
5. Requiring invasive mechanical ventilation
6. Death

The hospital recovery scale categories are defined below. For ease of categorization, the categories are defined from worst to best. A subject will be evaluated in the same ordering of the categories as below. Once a subject fulfils the criteria for a category, the category is assigned to the subject and the evaluation stops.

6. Death

- Subject died at any time on the day of assessment or earlier (all-cause mortality).

5. Requiring invasive mechanical ventilation

- Any oxygen support requiring intubation or extracorporeal oxygenation
- Invasive mechanical ventilation is used at any time on the day of assessment.

4. Admitted to the ICU, not requiring invasive mechanical ventilation

Subject met either of the 2 following criteria:

- In the ICU (and ICU level of care is required during the day of assessment)
- On the hospital ward, with or without supplemental oxygen, but deemed to require ICU level of care at any time during the day of assessment (e.g., not transferred to ICU due to bed availability)

Requiring ICU level of care is defined by:

- Some specific conditions:
 - Treatment of acute unstable arrhythmias
 - Treatment of complicated acid-base or electrolyte imbalances
 - Large volume resuscitation
 - Utilization of intravenous vasoactive medications
 - S/P cardiac arrest
 - Cardiogenic Shock
 - Acute myocardial infarct with complications
 - Cardiac tamponade
 - Acute congestive heart failure
 - Acute or imminent respiratory failure
 - Hemodynamic instability

- Diabetic ketoacidosis complicated by hemodynamic instability, altered mental status, respiratory insufficiency, or severe acidosis
 - Other conditions requiring specialized equipment and/or staff competencies only available in the ICU
3. Non-ICU hospitalization, requiring supplemental oxygen

Subject met either of the 2 following criteria:

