- Non-ICU hospitalized on the day of assessment (including readmittance), not ready for discharge during the whole day of assessment, as judged by the investigator and supplemental oxygen is required by the subject
- In the ICU but there is no medical reason to be in the ICU during the day of assessment, and supplemental oxygen is required by the subject

Requiring supplemental oxygen is defined by:

- Receiving supplemental oxygen through a face mask or nasal cannula and not being able to sustain a blood oxygen saturation of $\geq 94\%$ when breathing room air for 15 minutes at any time on the day of assessment.
- If supplemental oxygen was provided chronically pre-influenza infection (based on medical history), that amount of supplemental oxygen is exceeded to prevent hypoxia, tachypnea or dyspnea at some point on the day of assessment.
- Not receiving supplemental oxygen and either:
 - Having a blood oxygen saturation of $< 94\%$ when breathing room air for 15 minutes at any measurement on the day of assessment, or
 - In case of known pre-influenza $SpO_2 < 94\%$ (e.g., due to COPD), the current blood oxygen saturation on room air is lower than pre-influenza infection levels by at least 3%.

2. Non-ICU hospitalization, not requiring supplemental oxygen

Subject met either of the 2 following criteria:

- Non-ICU hospitalized on the day of assessment (including readmittance) and not ready for discharge during the whole day of assessment, as judged by the investigator
- In the ICU but there is no medical reason to be in the ICU during the day of assessment

1. Not hospitalized

Any of the following:

- Discharged from the hospital before the day of assessment
- Hospitalized at the day of assessment but ready for discharge on both the day of assessment and the day prior, as judged by the investigator (e.g., in case of lack of bed availability in a skilled nursing facility, lack of social support at home).

Notes: If a subject was discharged from the hospital “Against Medical Advice” on the day prior to the day of assessment, the subject will be considered as hospitalized (evaluating the other aspects of the HRS to define the correct category based on available data, e.g.: requiring supplemental oxygen, on the day of assessment). The hospital recovery scale category will be considered missing on subsequent days.

The HRS will be missing after a subject withdrew (except for withdrawal due to death) from the study.

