5.2.2. Estimand

The population of interest is hospitalized subjects between 13 to 85 years old with a confirmed influenza A infection.

The primary variable is the hospital recovery scale as assessed on Day 6 and will be compared between pimodivir and placebo on top of SOC. The hospital recovery scale is an ordinal mutually exclusive scale of six categories (death, requiring mechanical ventilation, requiring ICU, non-ICU hospitalized requiring supplemental oxygen, non-ICU hospitalized not requiring supplemental oxygen and non-hospitalized).

The intercurrent event of the use of influenza antivirals as part of SOC is handled in a treatment policy strategy as the primary endpoint is derived in the same way irrespective of the components of SOC. Treatment discontinuation is an intercurrent event that is also handled in a treatment policy strategy. Death as intercurrent event is handled in a composite strategy as it is one of the categories of the HRS. Other factors as for example bed availability that can influence the status of the subject are intercurrent events that are also handled with the composite strategy as the HRS accounts for the status of where the subject ‘should be’ instead of where the subject physically is.

The common odds ratio estimated by a proportional odds model is used as the population-level summary. If the assumption (by testing the parallel slopes for the treatment effect only) of the proportional odds would not hold for the treatment effect, the Van Elteren test will be used in a sensitivity analysis and the resulting p-value would be used in the formal testing. A second sensitivity analysis is conducted to handle missing data by an MAR/MNAR multiple imputations method. This is done for all missing HRS values on day 6 and separately for HRS values on day 6 that are missing due to COVID-19 and for HRS values that are missing not due to COVID-19.

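### The HRS missing-data rules can remove a known death or readmission from the Day 6 primary analysis after discharge against medical advice, or a known death after withdrawal for another reason

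*SAP*

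**What the plan says.** **Death.** SAP 5.2.1 defines category 6 as death from any cause on or before the assessment day. Categories are checked from worst to best, and checking stops at the first one met. Attachment 6 repeats the order: "First check if the subject falls in category 6 (has the subject died?) if not then we evaluate category 5". It codes category 6 by comparing the death date (DM.DTHDTC) with the assessment date, with no condition on withdrawal or discharge. SAP 5.2.2 adds: "Death as intercurrent event is handled in a composite strategy as it is one of the categories of the HRS".

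**Withdrawal.** SAP 5.2.1 states: "The HRS will be missing after a subject withdrew (except for withdrawal due to death) from the study". The matching note in Attachment 6 has no exception: "In case the subject withdrew from the study, the HRS will be set to missing from the next day onwards". Protocol 10.3 ("A subject will be automatically withdrawn from the study for any of the following reasons") lists loss to follow-up, withdrawal of consent or assent, and death.

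**Discharge against medical advice.** SAP 5.2.1 scores the subject as hospitalized on the day after discharge and as missing on later days. The footnote in Protocol 9.2.1.1 also makes later days missing. Attachment 6 works an example with discharge on Day 6: "Only in case 4 above we have a discharge against medical advice which would lead to missing values from day 8 onwards". None of the three makes an exception for a later death or readmission.

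**The concern.** The missing rules depend on how the subject left the hospital or the study, not on whether the Day 6 status is known. Discharge against medical advice is not one of the withdrawal reasons in Protocol 10.3, so these subjects stay in the trial. The note to the second Time and Events Schedule keeps readmitted subjects on schedule. Protocol 9.1.6 collects the date and cause of death after discharge. The Attachment 6 derivation already uses hospitalization (HO) records for ICU, ward and re-hospitalization days.

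The same subject could therefore count as dead in the all-cause mortality endpoint and as missing in the primary endpoint. Such scores would be removed because of events after randomization, and they lie at the worse end of the scale. If the losses differ by arm, the common OR is biased. No planned analysis of the primary endpoint restores the values: under SAP 5.2.3, multiple imputation is a sensitivity analysis that runs only above 10% missing (0.10 × 600 = 60 subjects at the planned size), and it would impute a score that is already known.

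**Working it through.** **1. Which subjects are exposed on Day 6**

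- *Discharge against medical advice on day D.* Day D+1 is scored and the HRS is missing from D+2. Day 6 is missing when D + 2 ≤ 6, that is D ≤ 4. SAP 5.2.3 agrees: its table of missing Day 6 values counts such discharges before Day 5. Example: discharge on Day 3 and death on Day 5, or an ICU stay on Day 6, gives missing.
- *Withdrawal because of death on Day 3.* The SAP 5.2.1 exception and the death-first order both give category 6. Nothing is lost.
- *Withdrawal for another reason on Day 3, death known to have occurred on Day 5.* The SAP 5.2.1 exception does not apply, so its wording gives missing. The death-first order gives category 6. The texts do not say which prevails.

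**2. The plan's own figure**

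Inputs from SAP 1.4 and 5.1.1: placebo distribution on Day 6 of 30/30/25/5/5/5%, common OR 0.62 (a 38% reduction), 1:1 allocation, two-sided 5%, 90% power.

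Applying 0.62 to each cumulative odds of a worse outcome gives a pimodivir distribution of 40.9/29.9/19.4/3.4/3.3/3.2%. With p̄ the average of the two arms, Σp̄³ = 0.0825.

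Whitehead: N = 12(1.960 + 1.282)² / [(ln 0.62)²(1 − Σp̄³)] = 12 × 10.51 / (0.2285 × 0.9175) = 601, against 600 stated. Power at 600 is 89.9%. The design reproduces.

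**3. Effect of losing known deaths**

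Expected Day 6 deaths are 300 × 0.05 = 15 on placebo and 300 × 0.0316 = 9.5 on pimodivir. I removed deaths from the expected counts, refitted the proportional odds model, and took power as Φ(|ln OR|/SE − 1.96). Here 1/SE² = n₁n₂(n₁+n₂)(1 − Σp̄³) / [3(n₁+n₂+1)²]. With no losses SE is 0.148 and power is 89.8%; the +1 term explains the small difference from 89.9%. An OR below 1 favours pimodivir, as in SAP 5.2.3.

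| Deaths lost (placebo / pimodivir) | Common OR | Power |
|---|---|---|
| 0 / 0 | 0.620 | 89.8% |
| 1 / 1 | 0.618 | 90.1% |
| 3 / 2 | 0.621 | 89.3% |
| 3 / 3 | 0.614 | 90.7% |
| 1 / 0 | 0.626 | 88.7% |
| 3 / 0 | 0.637 | 86.0% |
| 0 / 3 | 0.597 | 93.5% |

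With no true effect (15 deaths expected per arm), equal losses leave the OR at 1.00 and the one-sided error at 2.5%. Three losses on pimodivir only give OR 0.969 and a one-sided error of 4.0%.

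**4. How many subjects**

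The documents give no rate. For scale only, assume 2% to 4% of 600 leave or withdraw early and 10% to 20% of those die or are readmitted by Day 6: 600 × 0.02 × 0.10 = 1.2 to 600 × 0.04 × 0.20 = 4.8 subjects. These rates are assumptions. The count mixes deaths with readmissions, whereas the table treats every loss as a death.

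**The case against.** A reader might infer from the Attachment 6 note alone that any withdrawal, including a plain death on Day 3, blanks the Day 6 score, so that all early deaths leave the analysis. The documents do not support that. SAP 5.2.1 excepts withdrawal due to death and refers to Attachment 6 for the derivation details, so the two are read together; both check death first, and SAP 5.2.1 says checking then stops.

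The defence can go further and say the stop rule settles every death. That is a fair reading, but not the only one. The rule orders the six categories, while the missing rules are separate notes that can be programmed as an override. SAP 5.2.1 itself needed an explicit exception for one kind of death, which suggests its authors did not regard the order as sufficient.

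Three further points stand:

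- Data after loss to follow-up or withdrawal of consent may not exist. Only an optional safety visit is offered, and Protocol 16.2.3 does not settle whether survival status is collected after withdrawal. The readmission point therefore rests on subjects discharged against advice who remain in the trial.
- Nothing in the documents implies that losses would differ by arm.
- Missing Day 6 values are tabulated by reason, mortality is a separate endpoint, and the fundamental HRS (SAP 5.3.1.1) scores death and readmission on Day 6 with no such missing rule in its definition. The outcomes are not lost from reporting, but the primary analysis is not repaired.

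**Conclusion.** The point holds in a limited form. The rule on discharge against medical advice is stated in both documents without exception and can discard a known Day 6 outcome. For a known death after withdrawal for another reason, the SAP points both ways. Both are at odds with the composite handling of death, and the first also with the inclusion of readmission in the scale.

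The effect is probably small. It requires discharge against advice by Day 4, or an early withdrawal for another reason, followed by a known event by Day 6. Balanced losses barely move the OR or power. A one-sided loss of three deaths moves the OR by about 0.02 (0.637 − 0.620 = 0.017; 0.620 − 0.597 = 0.023) in a direction set by the arm. These sizes rest on the planning distribution and on assumed numbers of losses. They illustrate sensitivity and do not predict bias. The rule should still be corrected, because the remedy is cheap and a choice of precedence made after unblinding could be questioned.

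**What to change.** Before unblinding, state in SAP 5.2.1 and Attachment 6:

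1. Category 6 is assigned whenever DM.DTHDTC is on or before the assessment date, whatever the earlier withdrawal or discharge status. This overrides both missing rules.
2. After discharge against medical advice, days covered by a readmission HO record are scored from that record while the subject remains in the study.
3. Only the remaining days after withdrawal or such a discharge are set to missing, with the day after discharge scored as now.

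Align the footnote in Protocol 9.2.1.1, because it defines the primary endpoint and carries the same rule; an SAP edit alone would leave the two documents in conflict. The cost is a few sentences, the protocol alignment and a minor change to the derivation code. No new data collection is needed, since the rule uses only deaths and readmissions already recorded.

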2.1.3. Analysis Timepoints

For parameters that were assessed more than once daily, the analysis timepoint (ATPT) will be the timepoint as reported in the database. In case there are multiple records per planned timepoint take the last in time.

For hospitalized subjects we expect 3 assessments per day. If the timepoint is missing but the date time is known, then we impute as follows:

If date time is within [00:00, 11:00] then allocate the morning timepoint

If date time is within [11:01, 16:00] then allocate the midday timepoint

if date time is within [16:01, 23:59] then allocate the evening timepoint

For subjects that are discharged we expect only 1 vital sign assessment. Therefore in case the timepoint is filled in, we set it to empty.

For NEWS2, select for each of the parameters one record per timepoint as described above. The date and time of the NEWS2 will be derived from the last date time of each of the parameters and this will be used to allocate the NEWS2 to a phase. A subject received oxygen at the planned timepoint if the date time of the oxygen saturation measurement falls within the period that the subject received supplemental oxygen.

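### The two off-oxygen tests for hospital recovery scale category 3 in SAP Attachment 6 carry no date; coded as written they can score a desaturating inpatient 2 instead of 3

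*SAP*

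**What the plan says.** SAP 5.2.1 and Protocol 9.2.1.1 define requiring supplemental oxygen (category 3) by several routes. One is for subjects off oxygen: "Not receiving supplemental oxygen and either" a low room-air saturation that day or, where pre-influenza saturation was already low, a fall of at least 3% from that level.

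SAP Attachment 6 turns this into four coded tests:

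- **On oxygen (two tests, without and with chronic oxygen use).** Both require a concomitant medication (CM) record covering the day: "CMTRT=SUPPLEMENTAL OXYGEN and CMSTDTC <= date of assessment <= CMENDTC". The category 5 ventilation test has the same kind of window.
- **Off oxygen (two tests).** Both are coded as "No record in cm with oxygen supplementation". No date is attached to either.

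The rule printed above the first off-oxygen test is in the present tense and tied to the day of assessment: "Not receiving supplemental oxygen and Having a blood oxygen saturation of <94% when breathing room air for 15 minutes at any measurement". Attachment 6 also states that "The HRS is evaluated at baseline and per day, relative to the first study drug intake". Category 2 takes the remaining inpatients, and its code has no oxygen or saturation test.

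**The concern.** The on-oxygen and off-oxygen tests should complement each other on any given day. As written they do not. A subject whose only oxygen record lies on another day fails the on-oxygen tests because no record covers the day, and fails the off-oxygen tests because a record exists. The subject then drops to category 2 whatever the saturation.

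The rule sits at the boundary between categories 2 and 3 of the primary endpoint. The planning distribution puts 30% + 25% = 55% of placebo subjects in those two categories together, although only a part of category 3 could be affected. Attachment 6 also derives the baseline score, which is a covariate in the primary model (SAP 5.2.3). Under the literal text, a subject off oxygen and desaturating at baseline would be scored 2 at baseline if oxygen were first given later, so a post-baseline record would alter a baseline covariate.

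**Working it through.** **Step 1. Run the four tests under both readings.** The subjects are illustrative: on the ward, below category 4, not ready for discharge on both days, no chronic oxygen use, assessed on Day 6. *As written* means no CM oxygen record at any time. *Day-level* means no CM oxygen record covering Day 6.

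| Subject | As written | Day-level |
|---|---|---|
| CM oxygen Days 1–4; sustained-saturation item `N`, room-air SpO2 91% | 2 | 3 |
| CM oxygen Days 1–4; item `Y`, one room-air SpO2 of 91% | 2 | 3 |
| CM oxygen Days 1–4; pre-influenza SpO2 92%, now 88% (below 92 − 3 = 89) | 2 | 3 |
| Only CM oxygen record is Days 8–9; room-air SpO2 91% on Day 6 | 2 | 3 |
| Never on oxygen; room-air SpO2 91% | 3 | 3 |
| Oxygen ended on Day 6; item `N` (meets the first on-oxygen test) | 3 | 3 |

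The definition in SAP 5.2.1 gives 3 in every row. The readings differ only when an oxygen record exists on another day and none covers the assessment date.

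**Step 2. Reproduce the plan's sample size.** Inputs from SAP 1.4 and 5.1.1: placebo 30/30/25/5/5/5%; a 38% reduction, so OR 0.62; 1:1 allocation; two-sided 5%; 90% power.

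- Pimodivir distribution under OR 0.62: 40.9/29.9/19.4/3.4/3.3/3.2%.
- With p̄ the mean of the two arms, Σp̄³ = 0.0825.
- N = 12(1.960 + 1.282)² / [(ln 0.62)² (1 − 0.0825)] = 601.4, which matches the stated 600.
- Power at 600 = Φ(|ln OR|·√V − 1.96), with V = (600/12)(1 − Σp̄³) = 45.88. This gives 89.9%.

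**Step 3. Equal misclassification in both arms.** Move a fraction f of category 3 to category 2 in each arm, refit the proportional odds model to the expected proportions, and apply the same power formula. The values of f are assumptions.

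| f | Placebo categories 2 / 3 | Fitted OR | Σp̄³ | Power |
|---|---|---|---|---|
| 0 | 30.0% / 25.0% | 0.620 | 0.0825 | 89.9% |
| 10% | 32.5% / 22.5% | 0.622 | 0.0859 | 89.4% |
| 20% | 35.0% / 20.0% | 0.624 | 0.0909 | 88.9% |
| 40% | 40.0% / 15.0% | 0.626 | 0.1056 | 87.9% |

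For f = 40%: V = 50 × (1 − 0.1056) = 44.72, and Φ(0.468 × 6.687 − 1.96) = Φ(1.17) = 87.9%. A rank-score approximation starts slightly lower and falls similarly: 89.5% to 89.0%, 88.2% and 87.0% at f = 10%, 25% and 50%.

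**Step 4. Unequal misclassification under no effect.** Set the true OR to 1.0, apply f = 10/20/40% on placebo and a multiple of f on pimodivir. An OR below 1 favours pimodivir.

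| Pimodivir : placebo frequency | Apparent OR |
|---|---|
| 1.5 : 1 | 0.98 / 0.96 / 0.91 |
| 1.2 : 1 | 0.99 / 0.98 / 0.96 |
| 1 : 1.5 | 1.01 / 1.03 / 1.06 |

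The direction and size follow entirely from the assumed imbalance.

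**The case against.** The strongest reply is that the line is shorthand for not receiving oxygen that day. Four things support it.

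- The derivation is declared to be per day, and the line sits directly under a rule about the day of assessment. SAP 5.2.1 holds the governing definition; Attachment 6 supplies its details.
- Other daily conditions in the attachment are undated too, such as "SSTESTCD= 'REQICU' and SSSTRESC='Y" in category 4 and the room-air saturation bracket in the first off-oxygen test. Nobody would read those as applying to any day of the trial.
- Elsewhere the SAP treats oxygen use as time-specific. For NEWS2 (SAP 2.1.3), "A subject received oxygen at the planned timepoint if the date time of the oxygen saturation measurement falls within the period" of supplemental oxygen.
- Worked Case 9 shows CM oxygen as No together with not having returned to the prior oxygen level. SAP 5.3.1.1 takes that item from the oxygen supplementation form, which suggests that No means status on the day.

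Much of this stands, and it makes the day-level reading the more likely intention. It does not close the gap. Case 9 has missing saturation data, so it fails the off-oxygen tests under either reading. Cases 3 to 6 and 8 have CM oxygen as No and score as requiring oxygen, but none shows an earlier record that has ended. The authors did write the window into the other CM tests, so a programmer could take its absence here as deliberate. The other undated items concern a value recorded for a day; this one turns on the absence of any record.

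A reader might go further and infer that anyone ever given oxygen cannot reach category 3 off oxygen, that the primary comparison is biased towards pimodivir, or that the rule rewards stopping oxygen early. The documents support none of these. The first holds only under the literal reading. The second needs an arm imbalance that nothing in this double-blind trial's documents suggests. The third supposes that bedside decisions respond to a programming line.

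**Conclusion.** The specification of the primary endpoint is ambiguous at this point, and its literal form contradicts the definition it implements. Whether any subject would actually be misclassified depends on how the line is programmed, which the documents do not show.

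The exposure is limited to inpatients below category 4, not ready for discharge on both days, with an oxygen record on another day but none covering the assessment date, and desaturating on room air. Subjects never on oxygen, and those whose oxygen ended on the assessment day and who meet the first on-oxygen test, are scored 3 either way.

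The documents give no frequency for this group. If it made up 10% to 40% of category 3, equally in both arms, power would fall by about 0.5 to 2 percentage points and the odds ratio would hardly move. The case for correcting the text rests on having one unambiguous rule for the primary endpoint, more than on the expected numerical effect.

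**What to change.** In both off-oxygen tests of Attachment 6, replace the undated line with: no CM record of supplemental oxygen whose start date (CMSTDTC) is on or before the date of assessment and whose end date (CMENDTC) is on or after it. Use the same handling of missing end dates as in the on-oxygen tests, so that the two sets complement each other on each day.

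Add one worked example: oxygen recorded on earlier days and ended, no record covering the day, low room-air saturation, result requiring supplemental oxygen.

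Make the change before unblinding and check the program against it. It costs a few words and one table column, and needs no new data. If the day-level reading was always intended, the change only states it.
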